### **8.3.9. Medical Device Deficiencies**

The medical device being provided for use in some sub-studies is the prefilled syringe for SC injection; see the respective sub-study appendices for details on whether the medical device will be included in the sub-study. In order to fulfill regulatory reporting obligations worldwide, the investigator is responsible for the detection and documentation of events meeting the definitions of device deficiency that occur during the study with such devices.

The definition of a Medical Device deficiency can be found in [Appendix 8](#).

NOTE: Deficiencies fulfilling the definition of an AE/SAE will also follow the processes outlined in [Sections 8.3.1](#) through [8.3.4](#) and [Appendix 3](#) of the protocol.

#### **8.3.9.1. Time Period for Detecting Medical Device Deficiencies**

Medical device deficiencies or malfunctions of the device will be detected, documented, and reported during all periods of the study in which the medical device is used.

If the investigator learns of any device deficiency at any time after a participant has been discharged from the study, and such incident is considered reasonably related to a medical device provided for the study, the investigator or site staff will promptly notify the sponsor.

The method of documenting medical device deficiencies is provided in [Appendix 8](#).

#### **8.3.9.2. Follow-up of Medical Device Deficiencies**

Follow-up applies to all participants, including those who discontinue study intervention.

The investigator is responsible for ensuring that follow-up includes any supplemental investigations as indicated to elucidate the nature and/or causality of the deficiency.

New or updated information will be recorded on a follow-up form with all changes signed and dated by the investigator.

#### **8.3.9.3. Prompt Reporting of Medical Device Deficiencies to Sponsor**

Device deficiencies will be reported to the sponsor within 1 day after the investigator determines that the event meets the protocol definition of a medical device deficiency. Information will be provided to the sponsor as described in the IP Manual.

Any device deficiency that is associated with an SAE must be reported to Pfizer Safety within 24 hours upon the investigator's awareness as outlined in [Sections 8.3.1.1](#) and [8.3.1.2](#).

The sponsor will be the contact for the receipt of device deficiency information.

#### **8.3.9.4. Regulatory Reporting Requirements for Device Deficiencies**

The investigator will promptly report all device deficiencies occurring with any medical device provided for use in the study in order for the sponsor to fulfill the legal responsibility to notify appropriate regulatory authorities and other entities about certain safety information relating to medical devices being used in clinical studies.

The investigator, or responsible person according to local requirements (eg, the head of the medical institution), will comply with the applicable local regulatory requirements relating to the reporting of device deficiencies to the IRB/EC.

### 8.3.10. Medication Errors

Medication errors may result from the administration or consumption of the study intervention by the wrong participant, or at the wrong administration site, or at the wrong time, or at the wrong dosage strength, or from inadvertent exposure.

Exposures to the study intervention under study may occur in clinical trial settings, such as medication errors.

Safety Event	Recorded on the CRF	Reported on the CT SAE Report Form to Pfizer Safety Within 24 Hours of Awareness
Medication errors	All (regardless of whether associated with an AE)	Only if associated with an SAE

Medication errors include:

- Medication errors involving participant exposure to the study intervention;
- Potential medication errors or uses outside of what is foreseen in the protocol that do or do not involve the study participant.
- Incorrect study intervention taken by participant.
- Overdosing.

Such medication errors occurring to a study participant are to be captured on the medication error page of the CRF.

In the event of a medication dosing error, the sponsor should be notified within 24 hours.

Whether or not the medication error is accompanied by an AE, as determined by the investigator, the medication error is recorded on the medication error page of the CRF and, if applicable, any associated AE(s), serious and nonserious, are recorded on the AE page of the CRF.

Medication errors should be reported to Pfizer Safety within 24 hours on a CT SAE Report Form **only when associated with an SAE**.

### 8.4. Treatment of Overdose

Administration of any dose of sasanlimab greater than the assigned dose level at any scheduled administration visit will be considered an overdose.

Sponsor does not recommend specific treatment for an overdose for any of the study drugs.

In the event of an overdose, the treating physician should:

1. Provide the appropriate supportive treatment as clinically indicated.
2. Contact the medical monitor within 24 hours.
3. Closely monitor the participant for any signs of toxicity, AEs, and laboratory abnormalities for at least 6 months after the overdose.
4. Obtain a plasma sample for PK analysis with clear documentation of the time it is collected relative to the date of the last dose of study intervention, if requested by the sponsor (determined on a case-by-case basis).
5. Document the quantity of the excess dose as well as the duration of the overdose in the CRF.
6. Overdose is reportable to Safety only when associated with an SAE.

Decisions regarding dose interruptions or modifications will be made by the investigator in consultation with the medical monitor based on the clinical evaluation of the participant.

Instructions for treatment of overdose for the drugs to be administered in combination with sasanlimab will be specified in the respective sub-study appendices.

### **8.5. Pharmacokinetics**

The PK sampling schedule is specified in the respective appendix for each sub-study and may be modified based on emerging PK data. Additional PK samples may be drawn on discussion with sponsor (ie, to investigate a safety event, etc).

All efforts will be made to obtain the PK samples at the scheduled nominal time relative to dosing. However, the exact time of the sample collection will always be noted on the source document and CRF. If a scheduled blood sample collection cannot be completed for any reason, the missed sample time may be re-scheduled with agreement of clinical investigators, participant and sponsor.

PK samples will be analyzed using a validated analytical method.

Details regarding the collection, processing, storage and shipping of the PK blood samples will be provided to the investigator site prior to initiation of the trial. The samples must be processed and shipped as indicated to maintain sample integrity. Any deviations from the processing steps (eg, sample collection and processing steps, interim storage or shipping conditions), including any actions taken, must be documented and reported to the sponsor. On a case-by-case basis, the sponsor may make a determination as to whether sample integrity has been compromised. Any deviation from the specified sample handling procedure resulted in compromised sample integrity, will be considered a protocol deviation.

As part of understanding the PK of the study interventions, samples may be used for metabolite identification and/or further bioanalytical evaluation, as well as for other internal exploratory purposes. These data may not be included in the Clinical Study Report (CSR).

Samples collected for this purpose will be retained in accordance with local regulations and, if not used within this timeframe, may be destroyed.

#### **8.5.1. Blood for PK Analysis of Sasanlimab**

Blood samples (3-mL whole blood at each time point) will be collected for PK analysis of sasanlimab, as outlined in the respective sub-study SoAs. Refer to the Laboratory Manual for instructions for specific details on collection tubes, processing, and shipping.

#### **8.5.2. Blood for PK Analysis of Combination Target Agents**

Blood samples will be collected for PK analysis as described in the respective sub-study SoAs. Refer to the Laboratory Manual for instructions for specific details on collection tubes, processing, and shipping.

### **8.6. Pharmacodynamics**

Exploratory analyses may be performed in response to emerging data on possible interactions between study treatments.

As part of understanding the pharmacodynamics of the investigational product, samples collected in the sub-study may be used for evaluation of the bioanalytical method, as well as for other internal exploratory purposes. These data will not be included in the CSR.

The pharmacodynamic samples must be processed and shipped as indicated in the instructions provided to the investigator site to maintain sample integrity. Any deviations from the pharmacodynamic sample handling procedure (eg, sample collection and processing steps, interim storage or shipping conditions), including any actions taken, must be documented and reported to the sponsor. On a case-by-case basis, the sponsor may decide whether sample integrity has been compromised.

### **8.7. Genetics**

#### **8.7.1. Specified Genetics**

Genetic assessments for all sub-studies will be performed utilizing tumor and blood samples as collected and described in the respective sub-study SoAs.

*Biospecimen to confirm eligibility:* DNA samples may be analyzed for the purpose of confirming the presence of DNA alterations (eg, BRAFV600E) if required for enrollment to the study arm.

In the event of DNA extraction failure, a replacement genetic blood sample may be requested from the participant, or the participant's tumor biopsy may be used to confirm the presence

of the DNA alterations. See the Genetics section of the individual sub-studies for additional details of the eligibility assessments.

*Baseline tumor biopsy:* Whole exome sequencing of participant's tumor biopsy will be performed on qualifying specimens to characterize DNA alterations that may be associated with response to therapy. TCR sequence analysis may be performed on qualifying tumor biopsies to assess associations between tumor-associated TCRs and clinical outcomes.

*Blood for cell-free DNA analysis:* samples may be analyzed for epigenetic and/or genetic associations with clinical outcomes.

*Blood for specified genetic research:*

Whole genome sequencing of participants' blood samples collected prior to initiation of study therapy may be performed to confirm somatic vs germline nature of DNA alterations detected in matched tumor samples. Whole genome sequencing of samples may also be performed to characterize epigenetic modifications of DNA. Genetic variation at specific loci (such as FCGR genes) or epigenetic modifications in peripheral blood may also be assessed by targeted assays using PCR or NGS-based methods applied to white blood cells or cell-free DNA.

*Blood for TCR analysis:* A separate peripheral blood specimen will be collected to monitor the T Cell Receptor repertoire over the first 2 cycles of therapy according to the [SoA](#) of each sub-study.

The sequencing methods will not have been validated for diagnostic use to assess predisposition to genetic disease. Details on processes for collection and shipment of these samples can be found in the laboratory manual.

### **8.7.2. Banked Biospecimens for Genetics**

A 4-mL blood sample optimized for DNA isolation (Prep D1) will be collected as local regulations and IRBs/ECs allow.

Banked Biospecimens may be used for research related to the interventions and NSCLC. Genes and other analytes (eg, proteins, RNA, nondrug metabolites) may be studied using the banked samples.

See [Section 10.5](#) for information regarding genetic research. Details on processes for collection and shipment of these samples can be found in the laboratory manual.

### **8.8. Biomarkers**

Biomarker data collected by investigator sites as part of standard clinical practice may be recorded in the CRF. Such data may include but not be limited to PD-L1 status and presence or absence of alterations in genes such as BRAF, EGFR, ALK, ROS1, or KRAS.

Collection of samples for biomarker research is also part of this study. Results from some of the biomarker research may be provided to the investigator.

The following samples for biomarker research will be collected from participants as specified in the respective sub-study [SoA](#):

- If baseline tumor samples are required prior to initiation of study therapy, the tumor collection procedure date should be as close to the start of study therapy as clinically feasible, and not before start of systemic cancer therapy. Tumor samples collected prior to systemic cancer therapy may be acceptable in select cases upon consultation with the sponsor. If a suitable tissue sample is not otherwise available, then an FFPE tissue sample from a de novo biopsy must be obtained during the screening period. The tumor samples should be collected by resection or core needle biopsy; if these options are contraindicated, fine needle aspirates are allowed. Core biopsies should be performed using a minimum 18-gauge needle whenever feasible to preserve tissue integrity for histological and structural assessment. A minimum of 3 separate cores are requested from the same biopsy site for each biopsy procedure. Tumor tissue from FFPE cell pellet material or from bone biopsies is not adequate and should not be provided. Tumor biospecimens should be submitted in the form of a FFPE tumor tissue block. If FFPE tissue blocks cannot be provided, the tissue should be submitted as FFPE tissue sections that are 4-5 microns thick on unstained, unbaked, slides (Superfrost Plus Gold or equivalent) that are freshly cut (ie, cut no more than 30 days prior to shipment to the central laboratory).
- Blood samples will be collected from the start of screening as indicated in the respective sub-study [SoAs](#). The samples will be stored as whole blood, plasma, or serum.

Optional samples for biomarker research that should be collected from participants in the study as appropriate are the following:

- Sections of tumor samples that are collected after initiation of study therapy are requested for assessment of treatment-related changes in tumor phenotype or mechanisms of resistance.

Samples may be stored at a facility selected by the sponsor for a maximum of 10 years (or according to local regulations) following the last participant's last visit for the study.

### **8.8.1. Specified Gene Expression (RNA) Research**

RNA may be isolated from qualifying tumor and blood specimens. The isolated RNA may be subjected to next-generation sequencing in order to define transcriptome profiles associated with effect of study treatment or clinical outcomes.

Details on processes for collection and shipment of these samples can be found in the laboratory manual.

### **8.8.2. Specified Protein Research**

Tumor specimens will be analyzed by immunohistochemistry and/or immunofluorescence. The results may be used to confirm study eligibility as specified for the combination (*biospecimen to confirm eligibility*). Available tissue may be used to characterize quantity and location of cells and proteins that may be associated with effect of study treatment or clinical outcomes.

4-mL blood sample for protein analyses will be collected. The sample(s) will be analyzed for proteins and polypeptides that may be associated with effect of study treatment or clinical outcomes.

Details on processes for collection and shipment of these sample(s) can be found in the laboratory manual.

### **8.8.3. Specified Metabolomic Research**

4-mL blood sample for metabolomic analyses may be collected for analysis of metabolites that may be associated with effect of study treatment or clinical outcomes.

Details on processes for collection and shipment of these sample(s) can be found in the laboratory manual.

## **8.9. Immunogenicity Assessments**

Immunogenicity blood samples will be assayed for ADA using a validated assay. The sample analysis will follow a tiered approach of screening, confirmation, and titer determination. Samples tested positive for ADA will be further analyzed for NAb using a validated assay in compliance with Pfizer standard operating procedures. Additional details regarding the collection, processing, storage, and shipping of the blood samples will be provided in the Study Manual. As part of understanding the PK of the study drugs, samples may be used for additional characterization of an observed immunogenicity response and/or evaluation of the bioanalytical methods. These data will be used for internal exploratory purposes and will not be included in the clinical report. Samples collected for this purpose will be retained in accordance to local regulations and if not used within this timeframe, will be destroyed.

### **8.9.1. Immunogenicity Assessment of Sasanlimab**

Blood samples (6 mL whole blood at each time point) for evaluation of immunogenicity (ADA) of sasanlimab will be collected from all participants at the time points as outlined in the respective sub-study [SoAs](#).

## **8.10. Health Economics**

Health economics/medical resource utilization and health economics parameters evaluated in this study will be specified in the respective sub-study [SoAs](#) ([Section 12.8.5](#) for Sub-Study A).

### **8.11. End of Treatment (EOT) Visit**

Participants who discontinue study treatment will undergo the EOT visit and obtain assessments per the respective sub-study [SoA](#). The EOT assessments will be conducted at the visit that the participant is discontinued from study treatment or no longer than 1 week after the decision to discontinue the participant from study drug. The tumor assessments must be completed if not completed in the last 8 weeks and prior response is other than PD. Laboratory assessments must be completed if not completed in the prior 7 days.

If the EOT visit falls within 7 days of the 30-day follow-up visit, the EOT visit can be used to satisfy the requirements for both visits.

## **9. STATISTICAL CONSIDERATIONS**

Detailed methodology for summary and statistical analyses of the data collected in this study is outlined here and further detailed in a SAP, which will be maintained by the sponsor. The SAP may modify what is outlined in the protocol where appropriate; however, any major modifications of the primary endpoint definitions or their analyses will also be reflected in a protocol amendment.

### **9.1. Estimands and Statistical Hypotheses**

#### **9.1.1. Estimands**

For estimands refer to the respective appendix for each sub-study. For Sub-Study A, refer to [Section 12.3](#); for Sub-Study B, refer to [Section 13.3](#).

### **9.2. Sample Size Determination**

Approximately 375 participants are expected to be assigned to study intervention based on eligibility, assuming that 5 combinations will be initially explored in the umbrella study; refer to the respective sub-study appendix for the sample size determination for each sub-study.

#### **9.2.1. Phase 1b Dose Finding**

The total number of participants will depend on the number of dose levels and escalation and de-escalations needed to determine the MTD/RP2D of each combination and the number of participants evaluable for DLT at each dose level.

For details of each sub-study's Phase 1b dose finding refer to the respective appendix.

#### **9.2.2. Phase 2 Dose**

After the RP2D of a combination is determined, the study will proceed to Phase 2 to assess efficacy. Details of each sub-study's respective Phase 2 design and sample size is in an appendix.

### 9.3. Analysis Set

For purposes of analysis, the following analysis sets are defined:

Participant Analysis Set	Description
Full analysis set	The full analysis set includes all participants who receive at least 1 dose of study drug. Participants will be classified according to the treatment actually received.
Safety analysis set	The safety analysis set includes all participants who receive at least 1 dose of study drug. Participants will be classified according to the study treatment actually received. In a non-randomized study the full analysis set and safety analysis set are identical.
Per-protocol analysis set	The per-protocol analysis set is a subset of the full analysis set and will not include participants who do not meet criteria that could impact the key objectives of the study. These criteria will be pre-specified in the statistical analysis plan. The per protocol analysis set will be used for sensitivity analyses of the primary efficacy endpoint.
DLT-Evaluable analysis set	The DLT-evaluable analysis set includes all participants who receive at least 1 dose of study treatment in the Phase 1b and either experience DLT during the DLT-observation period or complete the DLT-observation period without DLT. Participants without DLTs receive less than 75% of the planned dose of each study drug in during the DLT observation period for reasons other than treatment-related toxicity are not evaluable for DLT. All participants deemed non-evaluable for DLT may be replaced.
Biomarker analysis set	The biomarker analysis set for each biomarker is a subset of the safety analysis set and includes all participants with at least 1 biomarker evaluated pre-dose.
Pharmacodynamic analysis set	The pharmacodynamic analysis set is a subset of the safety analysis set and includes participants with at least 1 biomarker evaluated pre- and post-dose.
Immunogenicity analysis set	The immunogenicity analysis set is a subset of the safety analysis set and includes participants who have at least 1 analyzed sasanlimab ADA/NAb sample.
PK analysis set	The PK concentration analysis set is a subset of the safety analysis set and will include participants who have at least 1 concentration measurement for the measured analytes related to the study drug (ie, sasanlimab, etc).

Participant Analysis Set	Description
	The PK parameter analysis set is a subset of the safety analysis set and will include participants who have at least 1 of the PK parameters of interest for the measured analytes related to the study drug (ie, sasanlimab, etc).

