**Non-Adherence to Treatment Schedule:**

10. Failure to receive at least 75% of the planned doses of each of the investigational products during the DLT observation period due to treatment-related toxicities

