### 6.1.1. Administration of Sasanlimab

Qualified and trained investigator site personnel will administer sasanlimab at a fixed dose of 300 mg once every 4 weeks CCI by SC injection to the abdomen of participants ; see the respective sub-study appendix for the dose of sasanlimab to be administered in each sub-study. The 300 mg Q4W dose will be administered by either 1 prefilled syringe or, if provided in vials, 3 SC injections will be administered. For the CCI dose, vials will be provided and 3 SC injections will be administered; the maximum volume per injection should be 2 mL. See [Section 8.2.7](#) for local site injection tolerability assessment.

Injections to the abdomen are preferred. If SC injections in the abdominal location are not possible, SC injections can be administered in a distributed manner in the thighs. SC injections in the upper extremities (eg, deltoid, upper and lower arm) are not permitted.

Study staff should refer to the IP Manual for specific instructions on the preparation, handling, and administration of the study intervention.

A cycle is defined as the time from Day 1 dose to the next Day 1 dose. Participants will receive a single dose of sasanlimab on Day 1 of each cycle. Each participant may receive sasanlimab until completion of study treatment, progression of disease, unacceptable toxicity, withdrawal of consent, participant no longer willing to participate in trial, end of study or study termination.

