#### Phase 1:

Primary Estimand (DLT): DLT rate estimated based on data from DLT-evaluable participants during the DLT-evaluation period (Cycle 1 – first 28 days of study treatment) in Phase 1b.

- Variable: Occurrence of DLTs.
- Analysis population: DLT-evaluable participants defined as participants who receive at least 1 dose of the combination study treatment in Phase 1b and either experience

DLT during the DLT-evaluation period or complete the DLT-evaluation period without DLT. Participants without DLTs who receive less than 75% of the planned dose of each study drug in Cycle 1 for reasons other than treatment-related toxicity are not evaluable for DLT. All participants deemed non-evaluable for DLT may be replaced.

- Population-level summary measure: DLT rate defined as the number of DLT-evaluable participants with DLTs in the DLT-evaluation period divided by the number of DLT-evaluable participants in the DLT-evaluation period.

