**Figure 2. Sub-Study A Design**

#### 12.4.1. Phase 1b Design

The sasanlimab dose will remain fixed for all dosing cohorts in the Phase 1b part of Sub-Study A.

Beginning with the starting dose level, cohorts of 3-6 participants will be enrolled, treated, and monitored during the 28-day DLT evaluation period (Cycle 1). Participants without DLTs who receive less than 75% of the planned dose of the study intervention in Cycle 1 for reasons other than treatment-related toxicity are not evaluable for DLT. A minimum of 3 DLT-evaluable participants will be required; additional participants will be enrolled in the specific enrollment cohort to replace participants who are not considered DLT-evaluable,

where required. When all DLT-evaluable participants treated in a given enrollment cohort have completed the DLT observation period or experienced a DLT, whichever occurs first, the posterior distribution for the risk of DLT for new participants at different dose levels for the combination of interest will be evaluated. The posterior distributions will be summarized to provide the posterior probability that the risk of DLT lies within the intervals shown below:

- Underdosing: [0, 0.16);
- Target toxicity: [0.16, 0.33);
- Excessive toxicity: [0.33, 1].

In addition to accumulating safety data and observed DLTs, decisions on further participant enrollment and dose level selection will be guided by the escalation with overdose control (EWOC) criterion. A combination dose may only be used for newly enrolled participants if the risk of excessive toxicity at that combination dose is less than 25% (0.25). Refer to [Section 12.10.6](#) for further details of the BLRM.

An RP2D below the MTD, or highest safe dose tested, may be determined based on other safety, clinical activity, PK, and pharmacodynamic data. Before expanding into Phase 2, safety will be confirmed in at least 9 DLT-evaluable participants treated at the RP2D for each combination.

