#### **Phase 1b:**

Primary Estimand (DLT): DLT rate estimated based on data from DLT-evaluable participants during the DLT-evaluation period (Cycle 1 – first 21 days of study treatment) in Phase 1b.

Variable: Occurrence of DLTs.

Analysis population: DLT-evaluable participants defined as participants who receive at least 1 dose of the combination study treatment in Phase 1b and either experience DLT during the DLT-evaluation period or complete the DLT-evaluation period without DLT. Participants without DLTs who receive less than 75% of the planned dose of each study intervention in Cycle 1 for reasons other than treatment-related toxicity are not evaluable for DLT. All participants deemed non-evaluable for DLT may be replaced.

Population-level summary measure: DLT rate defined as the number of DLT-evaluable participants with DLTs in the DLT-evaluation period divided by the number of DLT-evaluable participants in the DLT-evaluation period.

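### The DLT-evaluability rule excludes only participants under-dosed on each study drug, so a participant who gets the full Day 1 sasanlimab dose but little of the oral drugs still counts as DLT-free

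*Protocol*

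**What the plan says.** Four places in the protocol state who is not evaluable for DLT. All apply to participants without a DLT and to under-dosing for reasons other than treatment-related toxicity.

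- Section 9.3, DLT-evaluable analysis set: those who "receive less than 75% of the planned dose of each study drug".
- Section 12.3, Sub-Study A Phase 1 estimand: "Participants without DLTs who receive less than 75% of the planned dose of each study drug in Cycle 1".
- Section 13.3, Sub-Study B Phase 1b estimand: those who "receive less than 75% of the planned dose of each study intervention in Cycle 1".
- Section 12.4.1, Sub-Study A Phase 1b design: those who "receive less than 75% of the planned dose of the study intervention in Cycle 1", without the word *each*.

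A related rule is DLT criterion 10 in Section 4.3.3. It makes the following a DLT when treatment-related toxicity is the cause: "Failure to receive at least 75% of the planned doses of each of the investigational products during the DLT observation period".

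On the dosing schedule, Section 6.1.1 states: "Participants will receive a single dose of sasanlimab on Day 1 of each cycle". Section 6.6 allows no sasanlimab dose reduction. The DLT window is the first 28 days in Sub-Study A (Section 12.4.5) and the first 21 days in Sub-Study B (Section 13.4.5), which is one cycle in each. The DLT-evaluable set is the analysis population for the Phase 1b primary endpoint (Section 9.4.2).

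**The concern.** Taken literally, the exclusion requires a shortfall on all the drugs at once. One full sasanlimab dose on Day 1 is 100% of that drug for the whole window, so the condition then fails whatever happens to the daily oral drugs. Those are the drugs on which partial exposure in Cycle 1 is most easily accumulated.

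Such a participant is counted as a completed, DLT-free observation at a dose they largely did not take. The error runs one way, because only DLT-free participants are affected and the observed DLT rate can only be lowered. That rate feeds the BLRM in Sub-Study A and the mTPI rules in Sub-Study B. In Sub-Study A the DLT-evaluable count also gates Phase 2, which needs at least 9 evaluable participants at the RP2D (Section 12.4.1).

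**Working it through.** **1. The logic of the wordings**

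- Sections 9.3, 12.3 and 13.3: non-evaluable if drug 1 < 75% *and* drug 2 < 75% *and* drug 3 < 75%.
- Criterion 10: DLT if it is not true that every drug reached 75%, that is, if drug 1 < 75% *or* drug 2 < 75% *or* drug 3 < 75%.
- Section 12.4.1: below 75% of the study intervention. Section 12.6 uses that term for all three drugs together, and how to combine them is not stated.

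The word *each* gives opposite rules because in criterion 10 it stands under a negation. A shortfall on one drug is thus a DLT if toxicity caused it, and a clean non-DLT if something else did.

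**2. Exposure arithmetic**

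- Sasanlimab: 1 of 1 planned dose = 100% after a full Day 1 dose.
- 75% thresholds: encorafenib 0.75 × 28 = 21 doses; binimetinib 0.75 × 56 = 42 doses; axitinib 0.75 × 42 = 31.5 doses.
- Section 12.6.6.1 permits Sub-Study A interruptions for logistical reasons, with return within 14 days. Fourteen of 28 days leaves 14/28 = 50% of encorafenib and 28/56 = 50% of binimetinib. The participant is still not below 75% of each drug, so stays evaluable.

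**3. The decision rule (Table 30, Sub-Study B)**

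Table 30 gives escalate for 0/3. To reproduce this, assume a Beta(1,1) prior, so that the posterior is Beta(1,4). Unit probability mass is interval probability divided by interval length.

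- Under-dosing [0, 0.25): (1 − 0.75⁴)/0.25 = 0.6836/0.25 = 2.73
- Target [0.25, 0.35): (0.75⁴ − 0.65⁴)/0.10 = 0.1379/0.10 = 1.38
- Over-dosing [0.35, 1]: 0.65⁴/0.65 = 0.1785/0.65 = 0.27

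The largest is under-dosing, hence escalate, as the table says. With the same prior and an assumed 0.95 elimination cut-off, 92 of 93 cells in the rows for 0 to 5 DLTs match. The exception, 3 DLTs in 16, has no bearing here.

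**4. Effect of one under-exposed participant among three**

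Let p be the true DLT rate at full exposure and f the fraction of that risk kept by the under-exposed participant. Then P(0/3) = (1 − p)² × (1 − f·p). Setting f = 1 gives three fully exposed participants.

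| p | f = 1 | f = 0.5 | f = 0 |
|---|---|---|---|
| 0.30 | 0.343 | 0.416 | 0.490 |
| 0.35 | 0.275 | 0.349 | 0.423 |
| 0.45 | 0.166 | 0.234 | 0.303 |

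For p = 0.35: 0.65³ = 0.2746; 0.65² × 0.825 = 0.3486; 0.65² = 0.4225.

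**5. Six participants**

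Table 30 escalates at 0 or 1 DLT. With m fully exposed participants and the rest at zero risk, P(≤1) = (1 − p)^m + m·p·(1 − p)^(m−1). At p = 0.35 this is 0.319 for m = 6 and 0.428 for m = 5. At p = 0.30 it is 0.420 and 0.528.

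**The case against.** The best defence is that criterion 10 and the evaluability sentence were drafted as a pair, with the same 75%, the same window and the same *each*, separated only by cause. On that reading a shortfall on any drug is a DLT if caused by toxicity and makes the participant non-evaluable otherwise. Section 12.4.1 fits this, and the sentence in Section 9.3 is visibly garbled, which suggests a slip and not a chosen rule. This is plausible as to intent. But no passage states it for evaluability, and the literal wording stands in the analysis-set definition and in both estimands.

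Three stronger conclusions that a reader might draw are not supported:

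- *That the exclusion can never apply.* A missed or partial Day 1 sasanlimab dose can still trigger it; Sub-Study B gives that dose from vials as three injections. A participant who does not complete the window without a DLT is already outside the set. Toxicity-driven shortfalls fall under criterion 10.
- *That every dose decision is biased.* Dilution arises only when such a participant occurs and is counted. Decisions are also not mechanical. Section 12.10.6 treats the model's recommendation as guidance, Section 12.9.1.2 gives weight to safety data beyond DLTs, and Section 13.4.1 continues cumulative DLT evaluation in Phase 2.
- *That 42% is the expected effect.* It assumes negligible risk in someone who had a full sasanlimab dose, SEA-TGT as well in the triplet, and perhaps some oral drug. It is an upper bound for one such participant in three.

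**Conclusion.** The definition is wrong as worded, within limits. A participant who receives the full Day 1 sasanlimab dose, completes the DLT window and takes little of the oral drugs for non-toxicity reasons stays in the denominator as DLT-free. That conflicts with criterion 10 and with the wording of Section 12.4.1.

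If one of three participants in an mTPI cohort is in this position and the true DLT rate is 35%, the probability of an escalate decision at 0/3 goes from 27% to about 35% with half the risk retained, and to 42% at most. The number of such participants and their residual risk are assumptions; the protocol gives neither. The figures apply to Table 30 in Sub-Study B only. The Sub-Study A BLRM is pushed in the same direction, but the effect is not quantified here.

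The change should be made, because the definition sets the denominator of the Phase 1b primary endpoint. The defect does not by itself show that any dose decision would be wrong.

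**What to change.** In Sections 9.3, 12.3 and 13.3, replace *each study drug* (or *each study intervention*) with *any study drug*. A DLT-free participant below 75% of the planned dose of any component of their assigned combination, for reasons other than treatment-related toxicity, is then non-evaluable and may be replaced. Repair the grammar of the sentence in Section 9.3 at the same time. Put the same wording in Section 12.4.1, so that all four places agree with each other and with criterion 10.

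The cost is one word in three places and one aligned sentence, and possibly one or two replaced Phase 1b participants. Replacement is already provided for in Sections 9.3, 12.4.1 and 13.4.1.
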